#### **13.2** Five Fraction Treatment Group

#### Two-Stage Design and Sample Size Justification

The planned sample size of 13 total eligible subjects is based on Simon two-stage optimal design with an overall significance level of 0.05 and power of 90% (Simon R, 1989). The concept of this design is to permit early stopping when a moderately long sequence of initial failure occurs. The historical response rate to conventional radiation treatments is 35%[42]. This response rate comes from a subsequent analysis of the Dutch Bone Metastasis Study which looked at 800 cGy in one fraction vs 2400 cGy in multiple fractions. It represents combined complete and partial responses. This analysis details what the response rate to conventional radiation retreatment in the setting of prior irradiation to the treated area and thus is used as the historical control for this group. The statistical hypothesis tested is as follows:

H0:  $p \le 35\%$  vs. HA:  $p \ge 75\%$ , where p is response rate

Rejection of  $H_0$  means that further study of the test treatment should be carried out. Under the above hypotheses, the type I error is the false-positive rate in accepting an ineffective treatment and type II error is the false-negative rate in rejecting a promising treatment.

Stage 1 of the study will include 6 eligible subjects. If at least 3 of 6 eligible subjects respond, additional 7 subjects will be enrolled into stage 2 of the study. If the total number of patients who respond (among the 13 patients) is 8 or more, the null hypothesis above will be rejected in favor of the alternate hypothesis.

Under the null hypothesis ( $p \le 35\%$ ), the expected sample size of the trial is only 9.

The assumptions and specifications for Simon's two-stage design are detailed in the following table 2

Alpha -----> 0.05

Beta -----> 0.10

Response Probability of Historical Conventional Radiation Treatment (P0) ---> 0.35 Response Probability of Stereotactic Radiation Treatment (P1) ---> 0.75

#### Table 2. Power Calculation and Sample Size Calculation Table

Optimal Two Stage Design	Optimum Design
First Stage Sample Size (n1)	6
Upper Limit For 1st Stage Rejection of Stereotactic	
Radiation Treatment (r1)	2
Maximum Sample Size (n)	13
Upper Limit for 2nd Stage Rejection of Stereotactic	
Radiation Treatment (r)	7
Expected Sample Size If Response Probability = P0	8.47
Probability of Early Termination at P0	0.65

#### **13.3 Secondary Endpoints**

Secondary endpoints will be analyzed by the following methods. For overall survival Kaplan-Meier plots and median times will be reported. Time to functional decline will me measured with Kaplan-Meier plots and median times will be reported. Duration of pain response will be measured with Kaplan-Meier plots and median duration of pain response will be reported.

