#### 1.3 Vertebroplasty:

Currently, the management of metastatic spinal tumors in the neurologically intact patient includes radiotherapy alone or a combination of surgery and radiotherapy for tumor suppression, pain reduction, and spinal stabilization[17]. Extensive surgical treatment is often limited by a patient's poor general condition, the multifocal nature of the disease, or the patient's short life expectancy. Radiation therapy alone does not impart early spinal stability and, frequently, patients progress to develop further vertebral body height loss or progressive deformity[18]. Percutaneous vertebral augmentation procedures can be effective in preventing further vertebral body collapse and in improving pain relief.

Percutaneous Vertebroplasty (PV) is a minimally invasive fluoroscopically guided procedure aimed at augmenting the vertebral body by injection of polymethyl methacrylate (PMMA) Initially developed in France in the late 1980's to treat aggressive vertebral angiomas, vertebroplasty has gained widespread acceptance worldwide[19]. In the United States, it is predominantly used to treat osteoporotic compression fractures. Percutaneous kyphoplasty is a modification of PV. It involves the percutaneous placement of balloons into the vertebral body, followed by an inflation/deflation sequence to create a cavity prior to the cement injection. The PK procedure may restore VB height and reduce kyphotic angulation prior to PMMA injection[20]. Vertebroplasty has been shown to be effective in controlling pain secondary to compression fractures in over 90% of patients in prospective studies[21]. Significant improvement in quality of life and decreased oral analgesic usage has also been shown. Although not widely used in the United States, vertebroplasty for metastatic spine disease has been shown in multiple studies to be effective in controlling pain and improving quality of life. In one study, 97% of patients experienced decrease in pain within 48 hours of the procedure. In another study 73% of patients decreased their oral analgesic dose by 50% or more[22-25].

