#### 2.2 Secondary:

- 2.2.1 To determine the duration of pain response at the treated site(s) scored as the time of maximal pain relief to an increase of 2 on the VAS
- 2.2.2 To determine the functional preservation of improvement using the Brief Pain Inventory (BPI)
- 2.2.3 To prospectively assess patients quality of life (QOL) using the Functional Assessment of Cancer Therapy General (FACT-G) and patients utilities using the EuroQol (EQ-5D)
- 2.2.4 To determine the long term stability of the treated vertebral bone (such as fracture, sclerotic change, vertebral body height or mal alignment) by MRI, CT scan and plain radiographs.

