#### **11.6 Other Response Parameters**

- **11.6.1** Duration of Pain Response: The duration of pain response will be measure from the date that CR or PR was recorded to the date of increase in the VAS at the treated site to a score 2 points higher than the lowest VAS score recorded.
- **11.6.2** Time to Functional Decline: Time from study entry to a Zubrod  $PS \le 3$
- **11.6.3** Overall Survival: The survival time will be measured from the date of accession to the date of death. All patients will be followed for survival. Every effort should be made to document the cause of death.

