#### 11.7 Removal of Subject from Study

We will be following the patients for 3 years. Subjects can be taken off the study treatment and/or study at any time at their own request, or they may be withdrawn at the discretion of the investigator for safety, behavioral or administrative reasons. The reason(s) for discontinuation will be documented and may include:

- 11.7.1 Subject voluntarily withdraws from consent
- 11.7.2 Subject is unable to comply with protocol requirements.
- 11.7.3 Subject demonstrates disease progression to targeted site.
- 11.7.4 Subject experiences toxicity that makes continuation in the protocol unsafe.
- 11.7.5 Development of second malignancy that requires treatment, which would interfere with this study.
- 11.7.6 Treating physician judges continuation on the study would not be in the subject's best interest.
- 11.7.8. Subject becomes pregnant.
- 11.7.9 If a research subject cannot be located to document survival after a period of 2 years, the subject may be considered "lost to follow-up". All attempts to contact the subject during the two years must be documented and approved by the Data Monitoring Committee.

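### Sections 11.6.1 and 13.3 do not say how death before pain return is handled; the default censors it, and the median then exceeds the time responders live with pain controlled

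*Combined protocol and SAP*

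**What the plan says.** All references are to the combined protocol and SAP.

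- **Analysis (13.3).** "Duration of pain response will be measured with Kaplan-Meier plots and median duration of pain response will be reported". Nothing is added on censoring, competing events or death.
- **End of response (11.6.1).** The clock starts when a complete or partial response is noted. It then runs "to the date of increase in the VAS at the treated site to a score 2 points higher than the lowest VAS score recorded". A VAS rise is the only terminating event.
- **Objective (2.2.1).** Duration is "scored as the time of maximal pain relief to an increase of 2 on the VAS". Death is again not mentioned.
- **Death.** It is counted only under overall survival (11.6.3): "The survival time will be measured from the date of accession to the date of death". The same section has every patient followed for survival.
- **Follow-up (11.7).** "We will be following the patients for 3 years".

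**The concern.** The patients have metastatic cancer and are followed for three years, so some responders may die before their pain returns. A responder who dies with pain still controlled never meets the 11.6.1 event. An analyst applying 13.3 as written would normally censor that patient at death or at the last VAS. The curve then answers how long response would last if nobody died. That differs from how long responders live with their pain controlled, and also from what share of them see pain return.

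Reading the curve as a no-death quantity also requires death to be unrelated to the risk of pain return. That is doubtful, because progressing cancer can plausibly drive both.

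Duration is the first secondary objective, and section 1.4 presents durable pain control as part of the purpose of the combined treatment. If the rule is left open, it can also be chosen after the data are seen, and the choice changes the reported median.

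**Working it through.** **1. The plan's own figures.** The plan states no figure for duration of pain response, so there is none to reproduce. The Simon designs in 13.1 and 13.2 do reproduce:
- Single fraction: expected sample size 14.08 and early termination probability 0.746 under the null; type I error 0.0477, power 0.905.
- Five fraction: 8.47, 0.647, 0.0431 and 0.905.

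They concern the one-month response rate and do not use duration.

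**2. Inputs.** From the documents: the event is a VAS rise only (11.6.1, 2.2.1), the method is Kaplan-Meier with a median (13.3), and follow-up is 3 years (11.7). Assumed, because the documents give neither: a median time to pain return Mp and a median survival Md, each between 6 and 24 months and measured from the start of response, with independent constant hazards.

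**3. Formulas.** Let a = ln 2/Mp and b = ln 2/Md.
- Kaplan-Meier median with deaths censored: Mp.
- Median time alive in response (event = pain return or death): ln 2/(a + b) = Mp × Md/(Mp + Md).
- Ratio of the two: 1 + Mp/Md.
- One minus Kaplan-Meier at 12 months: 1 − exp(−12a).
- Cumulative incidence of pain return at 12 months, death competing: [a/(a + b)] × [1 − exp(−12(a + b))].
- Its long-run plateau: a/(a + b) = Md/(Mp + Md).

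**4. One case in full.** Mp = Md = 12. The Kaplan-Meier median is 12. The median alive in response is 144/24 = 6.0, so the ratio is 2. One minus Kaplan-Meier at 12 months is 0.50. Cumulative incidence is 0.5 × (1 − 0.25) = 0.375, or 0.38.

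**5. Range** (medians in months).

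| Mp | Md | KM median, deaths censored | Median alive in response | Ratio | 1 − KM at 12 mo | Cumulative incidence at 12 mo | Plateau |
|---|---|---|---|---|---|---|---|
| 6 | 6 | 6 | 3.0 | 2.00 | 0.75 | 0.47 | 0.50 |
| 6 | 24 | 6 | 4.8 | 1.25 | 0.75 | 0.66 | 0.80 |
| 12 | 6 | 12 | 4.0 | 3.00 | 0.50 | 0.29 | 0.33 |
| 12 | 9 | 12 | 5.1 | 2.33 | 0.50 | 0.34 | 0.43 |
| 12 | 12 | 12 | 6.0 | 2.00 | 0.50 | 0.38 | 0.50 |
| 12 | 24 | 12 | 8.0 | 1.50 | 0.50 | 0.43 | 0.67 |
| 24 | 6 | 24 | 4.8 | 5.00 | 0.29 | 0.16 | 0.20 |
| 24 | 24 | 24 | 12.0 | 2.00 | 0.29 | 0.25 | 0.50 |

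**6. What depends on the assumptions.** The direction does not. Adding deaths as events can only lower the response-free-of-event curve, and one minus Kaplan-Meier is never below the cumulative incidence. The size depends on them entirely.

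**7. Which summary can supply a median.** With Mp = 12, cumulative incidence levels off at 33% if Md = 6 and at 43% if Md = 9. It would never reach 50%, so it cannot replace the planned median. The composite of pain return or death can.

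**The case against.** **The censoring rule is not written.** A reader might infer that the plan chose to censor deaths. It did not: 13.3, 11.6.1 and 2.2.1 are silent. Censoring is the ordinary consequence of a VAS-only event, but it remains an inference. This stands, and it makes the defect an unstated rule with a foreseeable default.

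**Local durability is a legitimate target.** Objective 2.2.1 concerns response at the treated site, and for that question a curve with VAS rise as the only event is a recognised choice if independence is accepted. Overall survival is reported beside it. This is why the planned curve should be kept. It does not remove the need to label the curve, and two separate curves do not give the reader the time lived in response.

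**Mortality in this trial is not documented.** A reader might take "the patient's short life expectancy" in section 1.3 as evidence that early death will be frequent here. That phrase gives one of several limits on extensive surgery for metastatic spinal tumours in general. Enrolled patients must have Zubrod 0-2 and localised disease. The objection stands: frequent death is plausible background only, and no figure for the overstatement can be drawn from the documents.

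**The error does not all favour the treatment.** A reader might infer that the plan flatters it throughout. Censoring lengthens the apparent duration, but it also makes pain return look more common than it is. Section 13.3 does not promise a relapse percentage, though one can be read off the plotted curve.

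**Little rests on the endpoint.** It is descriptive and limited to responders, about 23 (0.80 × 29 = 23.2) and 10 (0.75 × 13 = 9.75) if the design alternatives hold. No test or stopping rule uses it. This stands and limits the weight of the point.

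**Conclusion.** The plan leaves the handling of death before pain return unstated, and its VAS-only event leads by default to censoring. Under that default, the reported median estimates duration as if death did not occur and is longer than the time responders live with pain controlled. One minus the curve exceeds the actual incidence of pain return. The overstatement of the median is a factor of 1 + Mp/Md. That is 1.25 to 5 over the assumed 6 to 24 months for each median, and it rests on independent constant hazards that the documents neither state nor support with rates.

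The documents do not support a reading in which the trial's main conclusion is at risk. The one-month response test, its two-stage boundaries and the sample sizes do not use this endpoint. The point is a cheap improvement to a descriptive secondary analysis.

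**What to change.** In 13.3, with a matching sentence in 11.6.1:

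1. Report the median time alive with response maintained (event = pain return or death, whichever comes first) as the duration summary.
2. Report the Aalen-Johansen cumulative incidence of pain return, with death as a competing event.
3. Keep the planned Kaplan-Meier curve, labelled as censoring deaths.
4. Say how a death some time after the last VAS is dated and classified, since VAS visits are six months apart after month 6.

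All of these need one agreed time origin. Section 2.2.1 starts the clock at maximal relief, whereas 11.6.1 starts it when a complete or partial response was recorded; the two should be reconciled in the same edit.

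The cost is a few sentences of text and a few lines of analysis code. VAS and death dates are already collected, and the sample size does not change. The downside is a shorter headline duration.

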#### 14.0 Data Safety Monitoring Plan

A data safety monitoring committee including radiation oncologists not participating in this trial will be formed to review toxicity endpoints and efficacy data. The data safety monitoring committee will review and verify all reported AE. In particular, this committee will scrutinize the grading of adverse events and the attribution to therapy previously assigned by the investigators. This panel will have access to patient information so as to have the ability to critically review toxicity events. This study will use this committee to perform ongoing safety assessment. Toxicities will be reported to the treating center's IRB and also to the University of Texas Southwestern IRB.

## Appendix I

## **STUDY PARAMETER TABLE**

	PreTreatment		During Treatment			Follow-Up (months after therapy)				
	Within 30 days of study entry		After last treatment	1	3	6	Every 6 months for three years			
Confirmation of Pathology	Х									
History/physical	Х	Х	Х	Х	Х	Х	Х			
Performance Status	Х			Х	Х	Х	Х			
MRI spine*	$X^1$			X1	X1	X 	X 			
CT spine*	$X^1$			$X^1$	$X^1$	X 	X 			
BUN, creatinine, CBC w/ platelets, PT/PTT INR	Х									
Informed consent	Х									
Tumor response evaluation	Х			Х	Х	Х	Х			
VAS at treated Site	Х		Х	Х	Х	Х	Х			
Adverse event evaluation		Х	Х	Х	Х	Х	X			
QOL Studies	Х		Х	Х	Х	Х	X			
(BPI, Fact-G, EQ-5D) Vertebroplasty	X	X 	1	x	x	x	(12 months only)			

 $*X^1$ : Per physician's discretion  $X^2$  : within one month of start of radiation treatment.

#### Appendix II

[figure not shown]
#### **ZUBROD PERFORMANCE SCALE**

- 0 Fully active, able to carry on all predisease activities without restriction (Karnofsky 90-100).
- 1 Restricted in physically strenuous activity but ambulatory and able to carry work of a light or sedentary nature. For example, light housework, office work (Karnofsky 70-80).
- 2 Ambulatory and capable of all self-care but unable to carry out any work activities. Up and about more than 50% of waking hours (Karnofsky 50-60).
- 3 Capable of only limited self-care, confined to bed or chair 50% or more of waking hours (Karnofsky 30-40).
- 4 Completely disabled. Cannot carry on self-care. Totally confined to bed or (Karnofsky 10-20).
- 5 Death (Karnofsky 0).

Pain slows healing. Help us keep your pain controlled. We want you to be as comfortable as possible.

[figure not shown]
El dolor retarda la curación. Ayúdanos a controlar su dolor. Queremos que se encuentre lo más confortable que pueda.

## **PAIN INTENSITY SCALE**

**JT SOUTHWESTERN** 

#### Appendix IV Brief Pain Inventory

provi		lease								lications / much relie
0% No Relie		20%	30%	40%	50%	60%	70%	80%	90%	100% Complete Relief
	e the on ered wi			t descr	ibes ho	ow, dur	ing the	past 2	4 hou	rs, pain ha
A.	Gene	ral Acti	vity							
0 Does Interf	ere	2	3	4	5	6	7	8		10 Completely Interferes
В.	Mood									
0 Does Interf		2	3	4	5	6	7	8		10 Completely Interferes
C.	Walki	ng Abil	ity							
0 Does Interf		2	3	4	5	6	7	8		10 Completely Interferes
D.	Norm	al Worl	k (inclu	des bo	th wor	k outsid	le the	home a	nd ho	usework)
0 Does Interf		2	3	4	5	6	7	8		10 Completely Interferes
E.	Relat	ions wi	th othe	r peopl	е					
0 Does Interf		2	3	4	5	6	7	8		10 Completely Interferes
F.	Sleep									
0 Does Interf		2	3	4	5	6	7	8		10 Completely Interferes
G.	Enjoy	ment o	f life							
0 Does Interf		2	3	4	5	6	7	8		10 Completely Interferes
			Ca	pyright 199 Pair Ali	1 Charles Researd rights re:	S. Cleelar h Group served.	nd, PhD			

#### Appendix V

#### FACT-G (Version 4)

Below is a list of statements that other people with your illness have said are important. By circling one (1) number per line, please indicate how true each statement has been for you during the past 7 days.

	PHYSICAL WELL-BEING	Not at all	A little bit	Some- what	Quite a bit	Very much
an	I have a lack of energy	0	I	2	3	4
693	I have nausea	0	I	2	3	4
GP2	Because of my physical condition, I have trouble meeting the needs of my family	0	1	2	3	4
un	I have pain	0	1	2	3	4
C14	I am bothered by side effects of treatment	0	I.	2	3	4
690	t feel ill	Ô	1	2	3	4
ur j	I am forced to spend time in bed	0	1	2	3	4

	SOCIAL/FAMILY WELL-BEING	Not at all	A little bit	Some- what	Quite a bit	Very much
681	I feel close to my friends	0	1	2	3	4
അ	I get emotional support from my family	0	1	2	3	4
G 22	f get support from my friends	0	1	2	3	4
08=	My family has accepted my illness	0	1	2	3	4
æ	I am satisfied with family communication about my illness	0	1	2	3	4
686	I feel close to my partner (or the person who is my main support)	0	1	2	3	4
21	Regardless of your current level of sexual activity, please answer the following question. If you prefer not to answer it, please check this box and go to the next section.					
637	I am satisfied with my sex life	0	1	2	3	4

95 Dagʻini Copyright (1987, 1997 3-10/08 Page 1 of 3

#### FACT-G (Version 4)

# By circling one (1) number per line, please indicate how true each statement has been for you during the past 7 days.

		EMOTIONAL WELL-BEING	Not at all	A little bit	Some- what	Quite a bit	Very much
	68	[ feel sad	0	1	2	3	4
ļ	O22	I am satisfied with how I am coping with my illness	0	1	2	3	4
	œ	I am losing hope in the fight against my illness	0	1	2	3	4
į	054	I feel nervous	0	1	2	3	4
	س	I worry about dying	0	1	2	3	4
	GTF	I worry that my condition will get worse	0	1	2	3	4

	FUNCTIONAL WELL-BEING	Not at all	A little bit	Some- what	Quite a bit	Very much
aP:	I am able to work (include work at home)	0	1	2	3	4
612	My work (include work at home) is fulfilling	0	1	2	3	4
GF)	I am able to enjoy life	0	1	2	3	4
CP4	I have accepted my illness	0	1	2	3	4
6E5	1 am sleeping well	0	1	2	З	4
660	I am enjoying the things I usually do for fun	0	1	2	3	4
697 }	I am content with the quality of my life right now	0	1	2	3	4
الحي معري						

## Appendix VI

By placing a checkmark in one box in each group below, please indicate which statements best describe your own health state today.

Mobility	
I have no problems in walking about	
I have some problems in walking about	
I am confined to bed	
Self-Care	
I have no problems with self-care	
I have some problems washing or dressing myself	
I am unable to wash or dress myself	
Usual Activities (e.g. work, study, housework, family or leisure activities)	
I have no problems with performing my usual activities	
I have some problems with performing my usual activities	
I am unable to perform my usual activities	
Pain/Discomfort	
I have no pain or discomfort	
I have moderate pain or discomfort	
I have extreme pain or discomfort	
Anxiety/Depression	
I am not anxious or depressed	
I am moderately anxious or depressed	
I am extremely anxious or depressed	

To help people say how good or bad a health state is, we have drawn a scale (rather like a thermometer) on which the best state you can imagine is marked 100 and the worst state you can imagine is marked 0.

We would like you to indicate on this scale how good or bad your own health is today, in your opinion. Please do this by drawing a line from the box below to whichever point on the scale indicates how good or bad your health state is today.

> Your own health state today

Best imaginable health state 100 Ŧ 9 0 7 0 6 50 **T** 4 з 2 Ŧ 0

Worst imaginable health state

3
